**This rule will be based on the distance between the last adequate TA date and the event date.**

Let D1 be the largest distance (relative to the last adequate TA date) that a patient can have a tumor assessment and not be classified as having missed an assessment. Let D2 be the largest distance (relative to the last adequate TA date) that a patient can have a tumor assessment and not be classified as having missed two assessments. If the distance exceeds threshold D1 or D2 then the analysis will assume one or two missing TAs, respectively.

The threshold D1 will be defined as the protocol specified interval between the TAs plus the protocol allowed window around the assessments. Similarly, the threshold D2 is defined as two

times the protocol specified interval between the TAs plus the protocol allowed window around the assessments.

As per protocol, post-screening assessments are expected to be performed every  $A=6$  weeks ( $\pm B=7$  days) from the first dose for the first 12 weeks of treatment ( $I=84$  days); except for first tumor evaluation for which the time-window allowed is day 42 +7 days from first dose, then every  $X=8$  weeks ( $\pm Y=7$  days) thereafter until disease progression, subject decision, withdrawal of consent, initiation of subsequent anticancer therapy, subject is lost to follow-up, death or defined end of study.

Therefore:

- if the last adequate tumor assessment before the event date is performed on or before study day 21 ( $=7*A/2$ ) then  $D_1=49 (=A*7+B)$  days and  $D_2=91 (=2*A*7+B)$  days;
  - This accounts for the scenario where the last adequate tumor assessment is the baseline assessment. This also allows for the rare instance where an additional assessment occurred early in the study.
- if the last adequate tumor assessment before the event date is performed between study day  $M+1$  (where  $M= I- (1.5*A)*7$ ) to study day  $N$  then  $D_1=A*7+2*B$  days and  $D_2=(A+X)*7+B+Y$  days;
  - Day  $N$  is calculated as  $N = I- (0.5*A)*7$ .
  - This accounts for the scenario where only the first scheduled assessments after the last adequate tumor assessment occur prior to month  $I$ .
- if the last adequate tumor assessment before the event date is performed between study day  $N+1$  and study day  $P$  then  $D_1=X*7+B+Y$  days and  $D_2=2*X*7+B+Y$  days;
  - Day  $P$  is calculated as  $P = I+ (0.5*X)*7$ .
  - This accounts for the scenario where only the last adequate tumor assessment occurs prior to month  $I/7$ .
- otherwise, when the last adequate tumor assessment before the event date is performed after study day  $P+1$ , then  $D_1=X*7+2*Y$  days and  $D_2=2*X*7+2*Y$  days.

Using the D2 definition above, an event is censored as occurring after  $\geq 2$  missing tumor assessments if the distance between the last adequate tumor assessment date and the event date is larger than D2.

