13.8.2. Analysis of Secondary Outcome Measures

The cORR based on central review, and ORR (for confirmed + unconfirmed responses) based on local radiologist/investigator-assessed tumor evaluations and central radiologist review will be provided with a corresponding Clopper-Pearson (exact) binomial 95% CI for the ES and FAS.

The Kaplan-Meier (KM) method used to describe OS will present median time with 95% CI and estimates at several time points (including 2, 4, 6, 8, 10 and 12 months). Subjects without a death date by the data cut-off date will be censored for OS at their last contact date.

PFS will be calculated for the FAS and summarized using the KM method. The corresponding median PFS as well as PFS rates at selected time points (e.g. 3 and 6 months) will be provided with a 95% CI.

Progressive disease and death from any cause will be considered as events. If death or PD is not observed, the PFS will be censored at the date of last adequate tumor assessment prior to the cutoff date. However, if a PFS event is observed after more than 1 missing or inadequate tumor assessment, it will be censored at the last adequate tumor assessment. If a PFS event is observed after a single missing or non-adequate tumor assessment, the actual date of event will be used.

Subjects who received a new anti-tumoral treatment (chemotherapy, hormonotherapy, radiotherapy, surgery or other anti tumoral treatment), whatever the type of treatment before their disease progression will be censored at the last adequate assessment prior to the start date of the new antitumoral treatment.

Additional sensitivity analyses examining alternative censoring rules could be applied and will be described in the SAP.

Analysis of DOR and TTR will be summarized using KM method in a similar way.

Secondary outcomes measures in the subgroup of Japanese subjects will be examined separately.

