17.6.2. Specifications by methods of measurements

- **Measurement of lesions**

All measurements should be recorded in metric notation, using calipers if clinically assessed. All baseline evaluations should be performed as close as possible to the treatment start and never more than 4 weeks before the beginning of the treatment.

- **Method of assessment**

The same method of assessment and the same technique should be used to characterize each identified and reported lesion at baseline and during follow-up. Imaging based evaluation should always be done rather than clinical examination unless the lesion(s) being followed cannot be imaged but are assessable by clinical exam.

Clinical lesions: Clinical lesions will only be considered measurable when they are superficial and ≥ 10 mm diameter as assessed using calipers (e.g., skin nodules). For the case of skin lesions, documentation by colour photography including a ruler to estimate the size of the lesion is suggested. As noted above, when lesions can be evaluated by both clinical examination and imaging, imaging evaluation should be undertaken since it is more objective and may also be reviewed at the end of the study.

Chest X-ray: Chest CT is preferred over chest X-ray, particularly when progression is an important endpoint, since CT is more sensitive than X-ray, particularly in identifying new lesions. However, lesions on chest X-ray may be considered measurable if they are clearly defined and surrounded by aerated lung.

CT, MRI: CT is the best currently available and reproducible method to measure lesions selected for response assessment. This guideline has defined measurability of lesions on CT scan based on the assumption that CT slice thickness is 5 mm or less. When CT scans have slice thickness greater than 5 mm, the minimum size for a measurable lesion should be twice the slice thickness. MRI is also acceptable in certain situations (e.g., for body scans).

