### 9.1.3. Durations and times

Some analysis may require the computation of a duration from a reference day to a post-reference day.

Duration will be defined in days (or in seconds, if applicable) as following:

- Duration (in days) = Date - Reference date + 1 day
- Duration (in seconds) = (DateTime) – (Reference DateTime) + 1 sec

Unless specified otherwise, durations of events (e.g., duration of treatment) will be calculated in days. Conversions to weeks, months, years will be days/7, days/30.4375, days/365.25, respectively.

The *onset day of AE* is calculated from the date of first study treatment administration up to the start date of the AE notification, as follows:

- If start date  $\geq$  Date of first administration: onset day = Date AE notification – Date of first study treatment administration + 1
- If start date  $<$  Date of first administration: onset day = Date AE notification – Date of first study treatment administration

*Study day* is defined in the following manner:

- On or after the start date of study treatment: the study day will be calculated as (date of safety assessment) – (start date of study treatment) + 1. Study day 1 will therefore be the first day of study treatment.
- Before the start date of study treatment: the study day will be calculated as (date of safety assessment) – (start date of study treatment).

*Time to event* is defined in the following manner:

- The time from event i to an event j (in days) will be calculated as (date of event j – date of event i) + 1

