**Table 8: Illustration of D1 and D2 Criteria**

If the last tumor assessment before the event date occurs between Study Days	D1	D2
1 – 21	49	91
22 – 63	56	112
$\geq 64$	70	126

*Example: For a patient with a tumor assessment SD at Day 21 (last tumor assessment before PFS event), and PD at the next tumor assessment on*

- *Scenario 1: Day 46 (i.e. 25 days after SD). Patient is classified as not having missed tumor assessment between both scans. PFS is not censored.*
- *Scenario 2: Day 76 (i.e. 55 days after SD). Patient is classified as having missed 1 tumor assessment between both scans. PFS event is not observed after more than 1 missing or inadequate tumor assessment. PFS is not censored.*
- *Scenario 3: Day 113 (i.e. 92 days after SD). Patient is classified as having 2 missing tumor assessments between both scans. PFS event is observed after more than 1 missing or inadequate tumor assessment. Using the D2 definition, PFS is censored at the last adequate tumor assessment (at SD scan).*

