**Table 12: Censoring rules for PFS**

In the below table, “new antineoplastic therapy” refers to any additional secondary antineoplastic medication or anti-cancer surgery or radiotherapy.

	Situation	Event Date	Outcome
No baseline tumor assessments			
A1	No baseline assessment and death after the second scheduled post-baseline tumor assessment, or no death	Date of first study treatment administration	Censored
A2	No baseline assessment and death on or before the second scheduled post-baseline tumor assessment	Date of death	Event
No post-baseline tumor assessments (without new antineoplastic therapy given)			
B1	Death on or before the second scheduled post-baseline tumor assessment	Date of death	Event
B2	Death after the second scheduled post-baseline tumor assessment or no death	Date of first study treatment administration	Censored
With baseline and post-baseline tumor assessments (without new antineoplastic therapy given prior progression or death without progression observed)			
C1	Progression with zero or one missed/inadequate tumor assessment prior to progression	Date of progression	Event
C2	Death but no progression, with zero or one missed/inadequate tumor assessment prior to death	Date of death	Event
D1	Progression but two or more consecutively missed/inadequate tumor assessments prior to progression	Date of last adequate tumor assessment*	Censored
D2	Death without progression, but two or more consecutively missed/inadequate tumor assessments prior to death	Date of last adequate tumor assessment*	Censored
E	No progression, no death	Date of last adequate tumor assessment*	Censored
F	Treatment discontinuation due to ‘Disease progression’ without documented progression, i.e. clinical progression based on investigator claim	N/A (not considered as an event, patient without documented PD should be followed for progression after discontinuation of treatment)	Information ignored
Initiation of new antineoplastic therapy given prior progression or death without progression observed			
G	New antineoplastic therapy started before progression or death	Date of last adequate tumor assessment prior to initiation of new antineoplastic therapy*	Censored
H	No post-baseline tumor assessment and new antineoplastic therapy started prior to a death	Date of first study treatment administration	Censored

\* tumor assessment with non-missing and non-unknown overall lesion response, as defined in section 9.3.

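### When baseline is the last adequate scan, the missed-scan rule counts from the scan date instead of first dose, so a week-12 progression after one missed scan can be censored before treatment began

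*SAP*

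**What the plan says.** SAP 9.3 (determination of missing adequate tumor assessments) states: "This rule will be based on the distance between the last adequate TA date and the event date". Two thresholds follow. D1 is the longest gap with no scan counted as missed, and D2 the longest gap with fewer than two counted as missed. If the last adequate scan fell on or before study day 21, D1 is 49 days and D2 is 91 days. The SAP adds: "This accounts for the scenario where the last adequate tumor assessment is the baseline assessment".

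Baseline imaging is allowed from Day −28 to Day −1 (Protocol 9.1.1). Protocol 17.6.2 asks for it "as close as possible to the treatment start and never more than 4 weeks before the beginning of the treatment". The scan schedule and PFS both run from first dose (SAP 9.3 and 6.3.2).

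Row D1 of SAP Table 12 (a row label, not the threshold) covers "Progression but two or more consecutively missed/inadequate tumor assessments prior to progression" and censors at the last adequate scan. Protocol 13.8.2, repeated in SAP 14.2.4, says: "If a PFS event is observed after a single missing or non-adequate tumor assessment, the actual date of event will be used".

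**The concern.** The 91-day limit allows for two six-week intervals and one scan window. It makes no allowance for the time between the baseline scan and first dose, yet the distance includes that time. A patient with a single missed or non-evaluable scan (week 6) who progresses on the scheduled week-12 scan can exceed 91 days only because baseline imaging was done early in screening. The progression then becomes a censored record dated before treatment, against the stated rule that such an event counts.

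The direction is always the same: early progressions leave the main PFS analysis, and PFS looks better. The handling is also uneven. With no post-baseline scan at all, Table 12 counts a "death on or before the second scheduled post-baseline tumor assessment" as an event. Row D2 has the same weakness as row D1: with a non-evaluable week-6 scan, a death around week 12 can be censored at baseline. The follow-up summaries in SAP 14.2.12 reuse these dates.

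**Working it through.** **Inputs**
- SAP 9.3: A = 6 weeks, B = 7 days, X = 8 weeks, Y = 7 days, I = 84 days.
- Baseline scan s days before first dose, s = 1 to 28 (Protocol 9.1.1 and 17.6.2).
- Distance is a plain date difference. The SAP's example, from a scan on day 21, reads "Day 46 (i.e. 25 days after SD", and 46 − 21 = 25.
- PFS time is a date difference plus 1 (SAP 9.1.3: "The time from event i to an event j (in days) will be calculated as" the later date minus the earlier date, plus 1).

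**Step 1: reproduce the SAP's thresholds**

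M = 84 − 1.5×6×7 = 21; N = 84 − 0.5×6×7 = 63; P = 84 + 0.5×8×7 = 112.

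| Last adequate scan | D1 | D2 |
|---|---|---|
| on or before day 21 | 42 + 7 = 49 | 84 + 7 = 91 |
| days 22 to 63 | 42 + 14 = 56 | 98 + 14 = 112 |
| day 64 onward | 56 + 14 = 70 | 112 + 14 = 126 |

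Table 8 reproduces exactly. The first branch adds one 7-day window and the others add two. One window is enough only if the starting point is fixed, as first dose is.

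**Step 2: week-6 scan missed, progression on study day d**

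Distance from baseline = (d − 1) + s. PFS time if censored at baseline = −s + 1. Correct PFS time = d days. Months = days / 30.4375.

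| d | Distance | Above 91 when | Allowed baseline days affected | PFS time assigned | Should be an event at | Distance from first dose |
|---|---|---|---|---|---|---|
| 77 | 76 + s | s ≥ 16 | 13 of 28 | −15 to −27 days | 2.5 months | 76 |
| 84 | 83 + s | s ≥ 9 | 20 of 28 | −8 to −27 days | 2.8 months | 83 |
| 91 | 90 + s | s ≥ 2 | 27 of 28 | −1 to −27 days | 3.0 months | 90 |

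Measured from first dose, none exceeds 91, so each is one missed scan and an event.

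**Step 3: does another row of Table 12 apply?** Rows A1 and A2 need no baseline scan. Rows B1, B2 and H need no post-baseline scan. Row G needs new therapy. This patient has a baseline scan, a week-12 scan and no new therapy, so row D1 applies. Table 8 gives no help, because its first row begins at study day 1 and omits every baseline scan.

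**Step 4: illustrative effect on the Kaplan-Meier estimate.** With k early events of 90 lost and no other censoring, the estimate after month 3 is 90S/(90 − k) instead of S.

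| True PFS S | k = 1 | k = 3 |
|---|---|---|
| 80% | 72/89 = 80.9% (+0.9 points) | 72/87 = 82.8% (+2.8) |
| 50% | 45/89 = 50.6% (+0.6) | 45/87 = 51.7% (+1.7) |

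**The case against.** - **Baseline may not be adequate.** SAP 9.3 defines an adequate assessment by a non-missing overall response, which a baseline scan does not have. But the same section expressly places baseline in this branch. If baseline did not count, row D1 would have no censoring date, so the text would still need repair.
- **The day count.** Week 12 can be read as 84 elapsed days, which is study day 85. The minimum gaps are then 15, 8 and 1 days and the assigned times run from −14, −7 and 0 down to −27. SAP 9.3 uses 84 as a study day when deriving M and N, and that convention is followed above. The one-day shift does not alter the conclusion.
- **The negative time is a symptom.** This stands. Censoring at first dose would give the same Kaplan-Meier curve, because either way the patient leaves before any event. The harm is that an event becomes a censored record, so a floor at first dose is not a sufficient repair.
- **Size and containment.** This also stands. The 1 to 3 patients are an assumption, and 90 is the Efficacy Set target, whereas PFS is also reported on the FAS. Each affected patient needs a missed or non-evaluable week-6 scan, progression near week 12 and an early enough baseline scan. The Table 13 sensitivity analysis counts these progressions as events, and SAP 8 treats PFS as exploratory. A sensitivity analysis does not make the main derivation correct.

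**Conclusion.** The concern holds. As written, SAP 9.3 with Table 12 row D1 can turn a progression after one missed scan into a censored record dated before first dose, contrary to SAP 14.2.4 and Protocol 13.8.2. For progression on study day 84 this happens when the baseline scan was 9 or more days before first dose. The date arithmetic rests only on the documents. The 0.6 to 2.8 points rest on the assumption of 1 to 3 patients in 90 and no other censoring.

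The fault is confined to the main PFS analysis (local and central) and the summaries that reuse its dates. cORR, DOR, the sample size and the decision rule are not touched. The thresholds after a post-baseline main-period scan (112 and 126 days) are sound. It should be corrected, but it does not threaten the trial's primary conclusion.

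**What to change.** 1. SAP 9.3: when the last adequate assessment is baseline, measure the distance from the date of first study treatment. Keep 49 and 91.
2. Table 12, rows D1 and D2: where censoring still applies and there is no adequate post-baseline scan, censor at the date of first study treatment. Rows A1, B2 and H already use that date, as do rows C1 and D1 of Table 15.
3. Table 8: begin the first row at baseline.

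These changes cost a few lines of SAP text and a small programming change.

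Two secondary points:
- Define an adequate assessment as one whose overall response is neither missing nor NE, in 9.3 and the footnotes to Tables 12 to 15, replacing the leftover term Unknown.
- Only if this rule is used for the end-of-extension analysis in Protocol 13.1, derive D2 from the patient's next two scheduled scans: 56 + 56 + 14 = 126, 56 + 84 + 14 = 154 or 84 + 84 + 14 = 182 days. Under 12-weekly scanning a single missed scan already gives 168 days, above 126. This item needs a per-patient lookup. The three analyses listed in SAP 6.6 do not include an end-of-extension analysis.
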